3.2 Rationale for study design, doses and control groups

An open-label, nonrandomised, single dose study design is used to assess the PK, safety, and tolerability of ceftaroline in patients with ESRD requiring intermittent haemodialysis. A group of healthy volunteers with normal renal function and similar demographics will be recruited to provide within-study reference data.

Both male and female patients and healthy volunteers will be screened for the study. The inclusion and exclusion criteria are defined so that the healthy volunteers selected for participation in the study are known to be free from any significant illness.

Ceftaroline fosamil is being developed for the treatment of serious bacterial infections including those caused by aerobic gram-negative and gram-positive pathogens. The extensive clinical programme has established 600 mg infused over 1 hour every 12 hours as an appropriate dose in healthy volunteers with normal renal function. Phase I studies in subjects with various degrees of renal impairment have indicated that it is appropriate to reduce the dose to 400 mg every 12 hours for patients with moderate renal impairment (CrCL: 50 to 80 mL/min). Data from a previous study in patients with ESRD undergoing intermittent haemodialysis (P903-18) has been used to propose that 200 mg every 12 hours as an appropriate dose in this group of patients. Therefore it is considered appropriate to test this dose in the current study. To obtain adequate PK data in the control group with normal renal function, it will be necessary to administer the normal dose of 600 mg.

In a previous study in patients with ESRD (Study P903-18) a single dose of 400 mg of ceftaroline fosamil resulted in a C_{max} and AUC for ceftaroline that were up to 77% and 2.6-fold higher than in the control group of healthy volunteers administered the same dose. However, in comparison with healthy volunteers administered the standard 600 mg dose the C_{max} and AUC values in ESRD patients were up to 4% and 80% higher. Since the dose in this study is 200 mg, the C_{max} and AUC values in the ESRD patients are not expected to exceed those observed in healthy volunteers administered 600 mg ceftaroline fosamil.

In Study P903-18, blood samples for plasma concentrations of ceftaroline fosamil, ceftaroline, and ceftaroline M-1 were collected up to 72 hours after start of investigational product administration (ESRD patients had PK draws up to 48 hours during predialysis period and up to 72 hours during after-dialysis period and normal subjects had PK draws up to 48 hours after start of infusion). In ESRD patients dosed before dialysis, 5 of 6 patients had no measurable ceftaroline concentrations at 48 hours postdose. In ESRD patients dosed after dialysis, 4 of

6 patients had measurable ceftaroline concentrations in the 48-hour sample; concentrations dropped to below the lower limit of quantification (BLQ) in all 6 patients at the 60-hour and 72-hour time points. There were no detectable concentrations in the 24-, 36-, and 48-hour samples of the healthy control volunteers. For ceftaroline M-1, in ESRD patients dosed before dialysis, all 6 patients had no measurable concentrations at 48 hours postdose. In ESRD patients dosed after dialysis, 3 of 6 patients had measurable concentrations in the 60-hour sample; ceftaroline M-1 concentrations dropped to BLQ for all 6 patients at the 72-hour time point. In healthy controls, 1 of 6 volunteers had a measurable M-1 concentration in the 24-hour sample and there were no detectable concentrations at the 36- and 48-hour time points. Considering the times of last measurable ceftaroline and ceftaroline M-1 concentrations, the washout period of at least 1 week for ESRD patients in the current study is adequate. In addition, the difference in PK sampling durations for ESRD patients (up to 48 hours) and healthy volunteers (up to 24 hours) is not expected to have a confounding effect on differences in $t_{1/2\lambda_z}$, if observed.

As the PK of the ceftaroline-related moieties has been shown to be linear, a single dose of ceftaroline fosamil is considered adequate to define the PK behaviour of ceftaroline fosamil, ceftaroline, and ceftaroline M-1. Mathematical projections from single dose to steady-state conditions will be used to develop administration guidelines for this group of patients.

To obtain adequate PK data in the control group with normal renal function, it will be necessary to give the normal dose of 600 mg. To remove the potential influence of study-specific factors influencing the results, a matched control group of healthy volunteers with normal renal function will be included in the study (Group 2), as recommended in the FDA and Committee for Medicinal Products for Human Use (CHMP) guidelines ([FDA Guidance for Industry 2010](#) and [CHMP Note for Guidance 2004](#)). To ensure that the age, weight, and gender distribution of Group 2 are as closely matched to Group 1 as possible (age to be within ± 5 years and weight to be within $\pm 20\%$ of Group 1), Group 2 will be recruited after **an appropriate number of subjects in** Group 1 have completed the study.

Considering the primary objective is a PK objective, in which outcomes are not subjected to bias in assessments and data interpretations, the open-label design is deemed appropriate. In addition, due to the nature of the study and the dose selection for ESRD patients undergoing intermittent haemodialysis versus healthy volunteers, randomisation is not applicable to the current study.

4. SUBJECT SELECTION CRITERIA

The principal investigator should keep a record, the subject screening log, of subjects who entered prestudy screening.

Each subject should meet all of the inclusion criteria and none of the exclusion criteria for this study. Under no circumstances can there be exceptions to this rule.

4.1 Inclusion criteria

For inclusion in the study, all subjects should fulfil the following criteria:

1. Provision of signed and dated, written informed consent prior to any study-specific procedures
2. Male and female (who are not pregnant or lactating) subjects aged 18 to 75 years (inclusive) with suitable veins for cannulation or repeated venipuncture
3. Females must have a negative pregnancy test at screening and Day -1 (admission to the study centre) and must not be lactating
 - Females of childbearing potential: Females of childbearing potential must have a negative serum pregnancy test and confirmed (by the investigator) use of a highly effective form of birth control (Section 5.1.1) for 3 months before enrolment and until 3 months after the last investigational product administration
 - Females of nonchildbearing potential: Females of nonchildbearing potential are defined as females who are either permanently sterilised (hysterectomy, bilateral oophorectomy, or bilateral salpingectomy but excluding bilateral tubal occlusion) or who are postmenopausal. Females will be considered postmenopausal if they are amenorrhic for 12 months without an alternative medical cause. The following age-specific requirements apply: Females under 50 years old will be considered postmenopausal if they have been amenorrhic for 12 months or following cessation of exogenous hormonal treatment and luteinising hormone (LH) and follicle-stimulating hormone (FSH) levels in the postmenopausal range. Females over 50 years old will be considered postmenopausal if they have been amenorrhic for 12 months or more following cessation of all exogenous hormonal treatment
4. Male subjects should be willing to use barrier contraceptives (ie, condoms with spermicide) from the first day of investigational product administration until 3 months after the last investigational product administration
5. Have a body mass index (BMI) between 18 and 35 kg/m² and weight between 50 and **110** kg

For inclusion in the study healthy volunteers with normal renal function must fulfil the additional following criterion:

6. Healthy volunteers should have CrCL by Cockcroft-Gault >80 mL/min

For inclusion in the study patients with ESRD must fulfil all the additional following criteria:

7. Stable physical condition, consistent with ESRD, based on the results of the medical history, vital signs, 12-lead ECG, and clinical laboratory evaluations performed within 3 weeks of the first investigational product administration. As a result of renal impairment or underlying disease, certain laboratory parameters may be outside the normal reference ranges
8. CrCL by Cockcroft-Gault of <15 mL/min **or on haemodialysis**
9. Patients who require haemodialysis 3 to 4 times per week and are receiving the same dialysis regimen for at least 1 month before screening
10. Haematocrit level higher than 30% at screening and baseline for each treatment period
11. Concomitant medications to treat underlying diseases or medical conditions related to renal insufficiency are allowed, except when specifically excluded by name or pharmacological class

4.2 Exclusion criteria

Subjects should not enter the study if any of the following exclusion criteria are fulfilled:

1. History of any clinically significant disease or disorder which, in the opinion of the investigator, may either put the subject at risk because of participation in the study, or influence the results or the subject's ability to participate in the study
2. History or presence of gastrointestinal, hepatic, or any other condition known to interfere with the absorption, distribution, metabolism, or excretion of drugs
3. Any clinically significant illness, medical/surgical procedure, or trauma within 4 weeks of the first investigational product administration
4. Any clinically significant abnormalities in clinical chemistry, haematology, or urinalysis results, as judged by the investigator
5. Any positive result at screening for serum hepatitis B surface antigen, hepatitis C antibody, and human immunodeficiency virus (HIV)
6. Any clinically important abnormalities in rhythm, conduction, or morphology of resting ECG that may interfere with the interpretation of QTc interval changes.
7. Prolonged QTcF **>500** ms, or shortened QTcF <340 ms, or family history of long QT syndrome
8. Known or suspected history of drug abuse, as judged by the investigator

9. Current smokers, or those who have smoked or within the previous **3** months. **Nicotine replacement products, eg, nicotine patch, nicotine chewing gum are allowed**
10. History of alcohol abuse or excessive intake of alcohol, as judged by the investigator
11. Positive screen for drugs of abuse (patients with ESRD using medications that may cause a positive drug screen will not be excluded, as judged by the investigator), or alcohol at screening or on Day -1 (admission to the study centre) prior to the first investigational product administration
12. History of severe allergy/hypersensitivity or ongoing allergy/hypersensitivity, as judged by the investigator, or history of hypersensitivity to drugs with a similar chemical structure or class to ceftaroline fosamil, eg, cephalosporins
13. Excessive intake of caffeine-containing drinks eg, coffee, tea, caffeine-containing energy drinks and cola (more than 5 cups of coffee or equivalent per day)
14. Use of drugs with enzyme-inducing properties such as St John's Wort within 3 weeks prior to the first investigational product administration
15. Plasma donation within 1 month of screening or any blood donation/blood loss >500 mL during the 3 months prior to screening
16. Has received another new chemical entity (defined as a compound which has not been approved for marketing) or has participated in any other clinical study that included drug treatment within 3 months of the first investigational product administration in this study. The period of exclusion begins at the time of the last visit of the prior study. Note: subjects who consented and were screened, but did not receive investigational product in this study or a previous phase I study, are not excluded
17. Previous enrolment in the present study
18. Involvement in the planning and/or conduct of the study (applies to both AstraZeneca staff and/or staff at the study centre)
19. Judgement by the investigator that the subjects should not participate in the study if they have any ongoing or recent (ie, during the screening period) minor medical complaints that may interfere with the interpretation of the study data or are considered unlikely to comply with the study procedures, restrictions, and requirements

For healthy volunteers with normal renal function the following are considered additional criteria for exclusion from the study:

20. **Any clinically significant abnormalities in vital signs as judged by the investigator**
21. Use of prescribed or nonprescribed medication including antacids, analgesics other than paracetamol/acetaminophen, herbal remedies, vitamins, and minerals during the 2 weeks prior to the first investigational product administration or longer if the medication has a long half-life. Occasional use of paracetamol/acetaminophen for minor pains and headache, and hormone replacement therapy for females are allowed

For patients with ESRD the following are considered additional criteria for exclusion from the study:

22. Vital signs, after 10 minutes supine rest:
- SBP: 90 to 200 mmHg
 - DBP: **50** to 100 mmHg
 - Pulse rate: <40 or **>110** bpm
23. Significant change or addition to routine medication (prescribed or over-the-counter) within 1 month of the first investigational product administration. Minor changes to medications that require frequent dose adjustment, such as insulin or analgesia, can be made up to 2 weeks prior to the first investigational product administration as agreed between the investigator and AstraZeneca
24. Receiving any dialysis treatment other than intermittent haemodialysis
25. Renal transplantation or renal carcinoma within 1 year before screening
26. Requiring immunosuppressive medications, including steroids
27. History of nephrectomy

The procedures for withdrawal of incorrectly enrolled subjects are provided in Section [5.3](#).

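### Exclusion criterion 22 contradicts itself: its pulse line names values that exclude, but its two blood-pressure lines name the interval between the limits

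*Protocol*

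**What the plan says.** Section 4.2 of the protocol opens with the rule for the whole list: "Subjects should not enter the study if any of the following exclusion criteria are fulfilled". Criteria 22 to 27 come under a further heading: "For patients with ESRD the following are considered additional criteria for exclusion from the study". The stem of the first of these is "22. Vital signs, after 10 minutes supine rest", followed by three lines:

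- "SBP: 90 to 200 mmHg"
- "DBP: 50 to 100 mmHg"
- "Pulse rate: <40 or >110 bpm"

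Section 4 says of the inclusion and exclusion criteria together: "Under no circumstances can there be exceptions to this rule". Section 5.3 repeats this. It adds that a subject enrolled in error is to be reported at once to the sponsor's physician, that treatment should be discontinued, and that safety assessments should continue.

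**The concern.** The three lines stand under one stem but run in opposite senses. The pulse line describes who is kept out. The two blood-pressure lines have the form of an acceptable range, which describes who may come in. The stem has no word that turns the ranges round.

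This criterion is the protocol's only numeric blood-pressure limit for Group 1. A site that follows the words would turn away patients whose pressures lie between the limits. A site that follows the apparent meaning would enrol patients who, on the words, fulfil an exclusion that allows no exceptions. In both cases the eligibility record for Group 1 does not match the written rule.

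**Working it through.** The protocol gives no figure to reproduce here, and no sample size or error rate is involved. The check is a reading of the text.

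**Inputs (all from the protocol)**

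- Section 4.2, opening sentence: any fulfilled exclusion criterion bars entry.
- Section 4.2, heading over criteria 22 to 27: the items are reasons to exclude an ESRD patient.
- Section 4.2, criterion 22: SBP 90 to 200 mmHg; DBP 50 to 100 mmHg; pulse below 40 or above 110 bpm.
- Section 4.1, inclusion 7: stable condition judged partly on vital signs, with no numeric limits.
- Section 4.2, exclusion 1: clinically significant disease that may put the subject at risk, in the investigator's opinion.
- Section 4.2, criterion 20: vital signs left to investigator judgement, for healthy volunteers only.

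**Step 1. The literal rule.** Taking each line as a separate reason to exclude, criterion 22 excludes if SBP is in [90, 200], or DBP is in [50, 100], or pulse is < 40, or pulse is > 110.

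The negation gives the patients it does not bar: SBP < 90 or > 200, **and** DBP < 50 or > 100, **and** pulse from 40 to 110.

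**Step 2. The rule that the pulse line suggests.** Exclude if SBP is < 90 or > 200, or DBP is < 50 or > 100, or pulse is < 40 or > 110.

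**Step 3. Compare the two on illustrative values.** These values are chosen only to show the logic.

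| SBP (mmHg) | DBP (mmHg) | Pulse (bpm) | Lines fulfilled literally | Literal result | Result under evident intent |
|---|---|---|---|---|---|
| 140 | 80 | 70 | SBP, DBP | Excluded | Not excluded |
| 210 | 110 | 70 | None | Not excluded by criterion 22 | Excluded |
| 80 | 45 | 70 | None | Not excluded by criterion 22 | Excluded |
| 210 | 90 | 70 | DBP | Excluded | Excluded |

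The first three rows are reversed. The fourth is not: when only SBP is outside its range, the DBP line still excludes the patient. The literal rule is therefore not a clean inversion of the intended one.

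**Step 4. Look for a single reading that repairs all three lines.**

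- Supplying a word such as outside in the stem puts the two blood-pressure lines right. The pulse line then becomes the wrong one, because it already names the tails.
- Requiring all three lines to hold together does not help. The criterion would then exclude only patients with both pressures inside their ranges and a pulse in a tail, and pressures outside the ranges would never exclude anyone.

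No reading of the stem makes the three lines agree.

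**Step 5. Look for a resolution elsewhere.** Inclusion 7 has no numbers, and criterion 20 does not apply to ESRD patients. No other section gives numeric blood-pressure limits for Group 1.

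**Step 6. Consider text extraction as the cause.** This is unlikely. The less-than and greater-than signs survive in the pulse line and in exclusion 7, and both blood-pressure lines contain the word to.

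**Step 7. Reach.** Group 1 is planned at 8 patients (synopsis; Section 3.1). If the site applies the rule in Step 2 strictly, every patient it passes has both pressures inside the ranges, and so literally fulfils the rule in Step 1. How the site applied the criterion, and the patients' actual pressures, are not in the document. That this covers all or nearly all of the 8 is an assumption.

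**The case against.** The strongest reply is that nobody will misread this. The pulse line shows the pattern, and a literal reading would turn away patients lying between the limits, so a site would query it before applying it. There is one study centre (Section 3.1), the sponsor reviews the protocol with site staff before the first subject enters (Section 9.2), and adherence is monitored during the study (Section 9.3). That stands as an argument about likelihood: literal application is improbable. It does not correct the text, and Sections 4 and 5.3 give the site no discretion to depart from it.

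Three stronger readings are tempting, and the document does not support them.

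- **That any patient outside a blood-pressure limit is let in.** Both pressures must lie outside their ranges before criterion 22 stops excluding (fourth row of the table). Even then, not being barred by criterion 22 is not admission. Inclusion 7 and exclusion 1 still apply, though by judgement and without numeric limits.
- **That Group 1 would lose PK data as protocol violators.** The PK analysis set in Section 12.1.2 does ask for freedom from major deviations and violations. The clause is qualified, on its natural reading, by whether they are believed to alter the drug's PK materially. Nothing in the document suggests that a pressure inside the stated ranges would do so, and no calculation in Section 11.2 uses this criterion.
- **That all 8 Group 1 patients are established breaches.** This depends on how the site applied the criterion and on the pressures of those enrolled, neither of which is known.

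**Conclusion.** The contradiction is real. Two of the three lines in criterion 22 run against the third and against the exclusion heading, and nothing else in the protocol resolves it. It goes beyond a clerical slip, because followed exactly it excludes any ESRD patient with either pressure inside its range.

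The realistic harm is limited: an eligibility rule without exceptions that each Group 1 patient enrolled with SBP or DBP inside its range literally breaches. That is assumed to be all or nearly all of the 8 planned, on the premise that the site follows the evident intent. The consequence is deviations and audit queries. Wrongful enrolment is improbable, and no biased PK estimate is shown.

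This is an internal inconsistency in wording, not a design choice. It should be corrected at the next amendment.

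**What to change.** Reconcile the SBP and DBP lines with the exclusion heading and with the pulse line. Either of two edits does this:

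- reword the two lines so that they name values outside the stated limits, in the same form as the pulse line; or
- take the two ranges out of the exclusion list and state them as ranges to be met in the inclusion criteria for ESRD patients.

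The limits themselves are for the sponsor to confirm, and no change to them is proposed here.

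The cost is a small wording change to one criterion in a protocol amendment. Sample size, procedures and analyses are unaffected.

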5. STUDY CONDUCT

5.1 Restrictions during the study

The following restrictions apply for the specified times during the study:

1. The healthy volunteers in Group 2 should fast from at least 4 hours before the clinical laboratory evaluations at screening and during the residential period. Fasting is not required for the follow-up visit

2. Eat and drink only the standardised meals and drinks provided (apart from water) during the residential period in the study centre (a renal diet will be served to patients with ESRD)
3. Abstain from consuming any of the following:
 - Alcohol from 72 hours before Day -1 (admission to the study centre), during the residential period, and for 72 hours before the follow-up visit
 - Energy drinks containing taurine or glucuronolactone eg, Red Bull from 72 hours before Day -1 (admission to the study centre), during the residential period, and for 72 hours before the follow-up visit
 - Caffeine-containing drinks during the residential period, apart from any provided as part of a standardised meal. Excessive intake of caffeine should be avoided between discharge from the study centre and the follow-up visit
 - Poppy seeds found in speciality bread from the time of providing informed consent until after the final medical examination at the follow-up visit
4. Abstain from smoking, and drugs of abuse from the time of providing consent until after the final medical examination at the follow-up visit
5. Subjects should refrain from strenuous physical activity, which is not within the subject's normal daily routine, from 7 days prior to Day -1 (admission to the study centre) until after the final medical examination at the follow-up visit
6. Abstain from blood or plasma donation until 3 months after the final medical examination at the follow-up visit
7. Male subjects should use a condom with spermicide to prevent pregnancy and drug exposure of a partner and refrain from donating sperm or fathering a child from the first investigational product administration until 3 months after the last investigational product administration

Use of concomitant medications is described in Section 5.6.

